6.7.3. Laboratory Evaluations

Data for the following haematology, biochemistry, and urinalysis analytes received from central laboratory are to be measured at the scheduled visits indicated in the study flowchart.

Table 9: Laboratory Tests

Haematology Test (SI unit)	Biochemistry Test (SI unit)	Urinalysis

 • Red Blood Cell Count ($10^{12}/L$) • Red Blood Cell Count indices: 
 ◦ Mean corpuscular volume (MCV) (fL) ◦ Mean corpuscular haemoglobin (MCH) (fmol/cell) ◦ Reticulocytes (%) • Hemoglobin (g/L) • Hematocrit (%) • White Blood Cell Count ($10^9/L$) • Differential WBC ($10^9/L$ and %) 
 ◦ Neutrophils ◦ Lymphocytes ◦ Eosinophils ◦ Basophils ◦ Monocytes • Platelet count ($10^9/L$) 	
 • Alkaline phosphatase (ALP) (U/L) • Alanine aminotransferase (ALT) (U/L) • Aspartate aminotransferase (AST) (U/L) • Total and direct bilirubin (umol/L) • Total protein (g/L) • Glucose (mmol/L) • Creatinine (mmol/L) • Blood Urea Nitrogen (mmol/L) • Calcium (mmol/L) • Potassium (mmol/L) • Sodium (mmol/L) • Troponin T (ng/mL) • C-reactive protein (mg/L) 	
 • Specific gravity • pH • Glucose • Protein • Blood • Ketones • Bilirubin • Urobilinogen • Nitrite • Leukocyte esterase by dipstick • Microscopic examination

In accordance with the baseline value definition in Section 5.1.2, the absolute and percentage change from baseline will be derived as follows:

Absolute change (unit) = (post-baseline value – baseline value)

Percentage change from baseline = $[(\text{post-baseline value} - \text{baseline value}) / \text{baseline value}] \times 100$

All laboratory data will be reported in SI units. All quantitative laboratory test values at each assessed timepoints will be compared with the relevant reference range in SI units and categorized as:

- Low: Below the lower limit of the reference range.
- Normal: Within the reference range (upper and lower limits included).
- High: Above the upper limit of the reference range.

For summaries that present the worst value with respect to the reference range at the participant level, low and high are each chosen in preference to normal values. For parameters with both low and high reference ranges, participants who have assessments within both low and high ranges will be counted within each category for worst value summary tables.

For analysis purposes, values preceded by a “<” or a “>” sign (i.e. those below or above the limits of quantification) will be considered equal to the lower or upper limit of quantification, respectively.

Laboratory values will be assigned toxicity grades, when available, using criteria based on the NCI CTCAE version 5.0 scale (i.e. interventions and non-laboratory result checks will not be performed). For NCI CTCAE grades where bidirectionality is present (e.g. Hemoglobin, Lymphocytes, Calcium, Potassium and Sodium), the two toxicities will be assessed separately. (eg. for a sodium value of 158 mmol/L, this would be considered as grade 3 for hypernatremia. The same value would be assigned grade 0 for the analysis of hyponatremia.)

Parameters whose CTCAE grade can be derived are the following:

Haematology Test	Biochemistry Test

• Absolute eosinophils (Eosinophilia)• Hemoglobin (Anemia)• Hemoglobin (Increased)• Absolute lymphocytes (Decreased)• Absolute lymphocytes (Increased)• Absolute neutrophils (Decreased)• Platelet count (Decreased)• White blood cell count (Decreased)• White blood cell count (Leukocytosis)	
• Alkaline phosphatase (ALP) (Increased)• Alanine aminotransferase (ALT) (Increased)• Aspartate aminotransferase (AST) (Increased)• Total Bilirubin (Increased)• Calcium (Hypercalcemia)• Calcium (Hypocalcemia)• Creatinine (Increased)• Glucose (Hypoglycemia)• Potassium (Hyperkalemia)• Potassium (Hypokalemia)• Sodium (Hypernatremia)• Sodium (Hyponatremia)

Laboratory data will be summarized by default descriptive summary statistics for continuous and categorical variables for the Safety Analysis Set by treatment group and overall, as follows:

- Observed values and percentage change from baseline at each assessed timepoint for each standard continuous laboratory parameter.
- Number and percentage of subjects with categorized shift (low, normal and high) values relative to the reference range at baseline compared to each post-baseline timepoint for haematology and biochemistry.

- Number and percentage of subjects with worst categorized (low, normal and high) values relative to the reference range.

For haematology and biochemistry:

- Number and percentage of subjects with worst NCI-CTCAE toxicity values.
- Number and percentage of subjects with categorized shift NCI-CTCAE toxicity values at baseline compared to each post-baseline timepoint.

Listings of all clinical laboratory data including derived absolute change from baseline will be provided for the Safety Analysis Set. Within each listing, laboratory values outside the normal ranges will be flagged as either high or low and NCI-CTCAE grading will be provided for applicable laboratory assessments.

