5.1 Inclusion Criteria

Participants are eligible to be included in the trial only if all of the following criteria apply:

Age

1. Males aged 18 years and above at the time of signing the informed consent.

Type of Participant and Disease Characteristics

2. Histologically or cytologically confirmed adenocarcinoma of the prostate.
3. Has undergone primary therapy for prostate cancer (radical prostatectomy and/or definitive external beam radiation and/or brachytherapy). Salvage external radiation therapy (XRT) following radical prostatectomy >6 months prior to Day 1 is allowed.

4. No further local therapy to prostate or systemic therapy for prostate cancer and no metastasis-directed therapy for PSA-positron emission tomography (PET) positive lesions planned within 4 months after the first dose of VTP-850.
5. Serum testosterone >175 ng/dL.
6. Nonmetastatic (M0) disease and no evidence of prostatic bed recurrence verified by whole body bone scintigraphy and either computed tomography (CT) or magnetic resonance imaging (MRI). Note that a positive PSMA PET does not exclude the participant if the conventional scans are negative.
7. Serum PSA of >0.3 ng/mL for participants with prior radical prostatectomy (with or without salvage radiotherapy), or serum PSA of 2 ng/mL above nadir for participants with prior external beam radiation or brachytherapy.
8. PSA doubling time \leq 12 months.
9. Not planning to start ADT for at least 4 months after Day 1.
10. Eastern Cooperative Oncology Group (ECOG) Score 0 or 1.
11. Baseline laboratory parameters must meet the following criteria:
 - Haemoglobin \geq 110 g/L
 - White cell count \geq 2.0 \times 10⁹/L
 - Absolute neutrophil count \geq 1.5 \times 10⁹/L
 - Lymphocytes \geq 0.9 \times 10⁹/L
 - Platelets \geq 100 \times 10⁹/L
 - Creatinine \leq 1.5 \times upper limit of normal (ULN) OR calculated creatinine clearance \geq 50 mL/min by the Cockcroft Gault formula
 - Total bilirubin \leq 1.5 \times ULN, (total bilirubin >1.5 \times ULN is acceptable if total bilirubin is fractionated and direct bilirubin < 35%)
 - Alanine aminotransferase \leq 1.5 \times ULN
 - Aspartate aminotransferase \leq 1.5 \times ULN
 - Troponin T within normal range
 - HbA1c <7 %

Sex and Contraceptive/Barrier Requirements

12. Agrees to the following during the trial and for at least 65 days after the last dose of VTP-850:

- Refrain from donating sperm

PLUS, either

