8.4.3 Clinical Laboratory Assessments

Scheduled clinical laboratory assessments will be performed and samples will be sent to a central laboratory, with the exception of troponin T which will be performed by local laboratories.

- Unscheduled or emergency laboratory assessments may be performed using a local laboratory if needed to ensure rapid delivery of test results, otherwise unscheduled study laboratory assessments will be done at the central laboratory.
- See [Appendix 2](#) for the list of clinical laboratory tests to be performed and the SoA ([Section 1.3](#)) for the timing and frequency.
- The investigator must review the laboratory report, document this review, and record any clinically significant changes occurring during the trial as an AE. The laboratory reports must be filed with the source documents.
- Abnormal laboratory findings associated with the underlying disease are not considered clinically significant unless judged by the investigator to be more severe than expected for the participant's condition.
- All laboratory tests with values considered clinically significantly abnormal after the first dose with VTP-850 in the trial should be repeated until the values return to normal or to baseline grade or are no longer considered to be required by the investigator or medical monitor.

If clinically significant abnormal safety laboratory values do not return to normal/baseline grade within a period of time judged reasonable by the investigator, the aetiology should be identified, and discussed with the Medical Monitor.

- If laboratory values from non-protocol-specified laboratory tests performed at the institution's local laboratory require a change in participant management or are considered clinically significant by the investigator (e.g., SAE or AE or dose modification), then the results must be recorded in the eCRF.

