11.2.2.2 Laboratory Safety Tests

Severity grading using CTCAE Version 5.0 will be assigned to laboratory safety values where applicable. Laboratory results in reported units and International System of Units (SI) units will be listed, including high and low flags, severity grades where applicable, the corresponding normal range and clinical significance.

Safety laboratory tests summaries will be based on results in SI units. Absolute and change from baseline results, including the worst change for each parameter for each participant, will be summarised using descriptive statistics.

Treatment-emergent, out-of-range results with the corresponding severity grade, normal ranges, baseline results and clinical significance will be listed separately. Shift tables of the CTCAE grades will be used to show changes from baseline at each timepoint and the worst change in each participant. The number of participants showing shifts of at least 2 severity grades will be summarised.

The number of participants with treatment-emergent clinically significant safety laboratory test results and safety laboratory test results of Grade 3 or 4 will be summarised.

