6.8.1. Pharmacokinetic Analysis

Not Applicable.

7. Changes in the Conduct of the Study or Planned Analysis

The change from baseline for electrocardiograms have been added as a primary endpoint for the primary objective of evaluating the safety of VTP-850 prime-boost regimens.

8. Appendices

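### SAP 6.7.3 drops the protocol's per-participant laboratory change summaries without declaring it, and the per-participant tables it keeps ignore baseline

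*SAP*

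**What the plan says.** Protocol 11.2.2.2 (Laboratory Safety Tests) commits to these summaries:

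- by-visit and worst-change grade shifts: "Shift tables of the CTCAE grades will be used to show changes from baseline at each timepoint and the worst change in each participant";
- a per-participant count: "The number of participants showing shifts of at least 2 severity grades will be summarised";
- the worst change of each parameter in each participant, as a continuous summary;
- the number of participants with treatment-emergent clinically significant results, and the number with Grade 3 or 4 results.

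SAP 6.7.3 (Laboratory Evaluations) plans by-visit observed values and percentage change. It also plans by-visit shift tables from baseline, for range category and for CTCAE grade. At participant level it plans two summaries: "Number and percentage of subjects with worst categorized (low, normal and high) values relative to the reference range" and "Number and percentage of subjects with worst NCI-CTCAE toxicity values". For the range summary, "low and high are each chosen in preference to normal values". Listings show all values, absolute change from baseline, range flags and grades.

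SAP Section 7, which records changes to the planned analysis, has one entry: "The change from baseline for electrocardiograms have been added as a primary endpoint".

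Protocol 5.1, criterion 11, admits men with ALT, AST or creatinine up to 1.5×ULN. A total bilirubin above 1.5×ULN "is acceptable if total bilirubin is fractionated and direct bilirubin" is below 35%. Exclusion criterion 4 in Protocol 5.2 states that Gilbert's syndrome does not exclude.

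**The concern.** Laboratory results are part of the primary endpoint. SAP 2.2.1.1 lists the number and proportion of participants with clinically significant laboratory values and refers to Section 6.7 for the details, but Section 6.7.3 contains no such count.

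The one-row-per-man tables that remain answer a different question from the protocol's. The protocol asks how far each man moved from his own baseline. The SAP asks how extreme his values were, whatever they were at entry. With six men per regimen in Cohorts 2 and 3, one man in the wrong row changes the picture. Raised liver tests are a named potential risk of IV MVA-PCAQ (Protocol 2.3.1, Table 3), and Protocol 4.1.3 prefers the IV route for Phase 2 if both routes have acceptable safety.

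**Working it through.** The plan gives no figure to reproduce here. The check compares the two documents item by item and then tests what the planned tables can and cannot show.

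**Step 1: protocol item against SAP item**

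| Protocol 11.2.2.2 | SAP 6.7.3 |
|---|---|
| Grade shift at each timepoint | Kept |
| Grade shift, worst change per participant | Absent |
| Participants with a shift of 2 or more grades | Absent |
| Worst change per parameter per participant | Absent (by-visit percentage change only) |
| Participants with treatment-emergent clinically significant results | Absent |
| Participants with Grade 3 or 4 | Readable from the worst-grade table, with no baseline reference |

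None of the absences is in SAP Section 7. The loss is specific to laboratory data: SAP 6.7.4 keeps the worst change per participant for vital signs and uses the word post-baseline.

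**Step 2: a stable abnormality allowed at entry**

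The SAP defines High as above the upper limit of the reference range. ALT between 1 and 1.5×ULN is eligible and is High. If it never changes, the worst category is High. In a cohort of six, one such man gives 1/6 = 16.7%. Limiting the table to post-baseline values would not remove him, because he is still High after dosing. Only crossing with baseline does, by placing him in the High-to-High cell.

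**Step 3: what each SAP grade table misses alone** (hypothetical grades, six men, nine post-baseline visits)

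- Two men stable at Grade 1 from entry, or two men going from Grade 0 to Grade 1: the worst-grade table shows Grade 1 in 2/6 both times. Men who worsened: 0/6 or 2/6.
- One man up two grades at three visits, or three men each up two grades at one different visit: the by-visit tables show 1/6 at each of three visits both times. Men with a shift of two or more grades: 1/6 or 3/6.

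In the first pair the by-visit tables tell the cases apart, and in the second the worst-grade table does. So the two must also be tested together.

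**Step 4: both SAP grade tables together** (hypothetical grades; three visits shown, no change from baseline at the others)

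| Man | Baseline | Case E, visits 1, 2, 3 | Case F, visits 1, 2, 3 |
|---|---|---|---|
| a | 0 | 2, 2, 0 | 2, 0, 1 |
| b | 0 | 0, 0, 1 | 0, 2, 0 |
| c | 1 | 2, 1, 1 | 2, 2, 1 |
| d | 1 | 1, 2, 1 | 1, 1, 1 |
| e, f | 0 | 0, 0, 0 | 0, 0, 0 |

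- By-visit shifts, same in E and F. Visits 1 and 2: 0→0 three men, 0→2 one, 1→1 one, 1→2 one. Visit 3: 0→0 three, 0→1 one, 1→1 two.
- Worst grade, same in E and F: Grade 0 two men, Grade 1 one, Grade 2 three.
- Shift of two or more grades: E, man a only, 1/6. F, men a and b, 2/6.
- Any worsening: E, men a to d, 4/6. F, men a, b and c, 3/6.

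The full set of SAP grade tables is identical in the two cases, and the protocol's count is not.

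**Step 5: reach of the by-visit tables**

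With dosing on Days 1, 29 and 57, the laboratory windows in SAP Table 5 leave Days 2–10, 28, 56 and 105–165 uncovered: 9 + 1 + 1 + 61 = 72 of the 194 days from Day 2 to Day 195, or 37%. An unscheduled value on one of those days enters no by-visit shift table.

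**The case against.** The strongest reply is that worsening is already visible. The grade-shift bullet directly follows the worst-grade bullet, and a range-shift table is planned as well. Each window takes its worst value and includes unscheduled tests. Table 5 covers Days 2–27 after each scheduled boost without a gap, which is the period of interest for liver tests after IV dosing. Listings give change from baseline and grade, and six men per cohort can be read by eye. Clinically significant changes are also recorded as adverse events (Protocol 8.4.3). All of this stands, and it makes the point one of presentation and traceability, not of lost data. It does not supply the protocol's per-participant counts, and the listing described in 6.7.3 does not mention clinical significance. The table shells are not in the documents and may contain more, but the SAP text does not commit to it.

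A reader might infer four stronger things that the documents do not support:

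- *Real worsening goes uncounted.* It is counted by visit. What is missing is the count of men over the whole follow-up.
- *Entry abnormalities are reported as toxicity.* That follows only for range category. Whether an entry value also receives a CTCAE grade depends on cut-offs that the documents do not give.
- *Severe local-laboratory values never reach the worst-value tables.* Protocol 8.4.3 does say "Unscheduled or emergency laboratory assessments may be performed using a local laboratory if needed to ensure rapid delivery of test results", but its eCRF clause concerns tests that the protocol does not specify. Appendix 2 asks for a central sample at the same time when a local one is required.
- *The choice of Phase 2 regimen rests on this table.* Protocol 4.1.1 gives that choice to the SMC, on cumulative safety data and the DLT criteria.

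**Conclusion.** The point holds. Four per-participant laboratory summaries promised in Protocol 11.2.2.2 are missing from SAP 6.7.3 and not declared in Section 7, and the two per-participant tables that remain make no reference to baseline.

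Its size: each eligible man with a stable out-of-range value adds 1/6 = 17% to the worst High or Low row of a six-man cohort with no change in his laboratory values. The grade tables can be identical while the two-grade count differs (1/6 or 2/6 in the constructed case). The 17% rests on the SAP's own definition of High and on one such man being enrolled; the documents do not say how many there are. The grade examples are hypothetical and show what is possible, not what is likely.

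The analysis is descriptive and most of the information can be rebuilt from listings, so this is not a threat to the trial's conclusions. It should still be corrected, because it concerns a primary safety endpoint and costs very little.

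**What to change.** In SAP 6.7.3:

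1. Define worst as the worst post-baseline value, using all scheduled and unscheduled results, whether or not they fall in a visit window.
2. Replace the two stand-alone worst-value tables with cross-tabulations of worst post-baseline against baseline, one for range category and one for CTCAE grade. Keep the existing rules for both-direction values.
3. Restore from Protocol 11.2.2.2 the number of participants with an increase of two or more grades, the worst change per parameter, and the number with treatment-emergent clinically significant results. Report the last alongside the Grade 3–4 count, and state what treatment-emergent means for a laboratory value.
4. If any of these is to be left out on purpose, say so in SAP Section 7 with the reason.

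The by-visit shift tables and the listings stay as they are. The cost is SAP text and one revised table shell, with no new data collection.

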6.7.4. Vital Signs

The analyses described below will be conducted for the following vital signs assessments respectively:

- systolic blood pressure (mmHg);
- diastolic blood pressure (mmHg);
- pulse rate (bpm);
- respiration rate (breaths / min);
- body temperature (°C).

In accordance with the baseline value definition in Section 5.1.2, the absolute change from baseline will be derived as follows:

Absolute change (unit) = (post-baseline value – baseline value)

Vital sign values will be considered as potentially clinically important (PCI) if they meet criteria listed in Table 10.

Table 10: Criteria for Potentially Clinically Important Vital Signs Parameters

Vital Sign	Criteria for observed value	Flag
Pulse Rate	<45 bpm	Low (L)
	≥45 and <120 bpm	Normal
	≥120 bpm	High (H)
Systolic Blood Pressure (SBP)	<90 mmHg	Low (L)
	≥90 and <160 mmHg	Normal
	≥160 mmHg	High (H)
Diastolic Blood Pressure (DBP)	<55 mmHg	Low (L)
	≥55 and <100 mmHg	Normal
	≥100 mmHg	High (H)

The following will be summarized by treatment group and overall for the Safety Analysis Set:

- Observed values and absolute change from baseline at each assessed timepoint for each standard vital sign parameter using default summary statistics for continuous variables;
- The worst absolute change (most extreme value, either increase or decrease) for each variable for each participant will be summarized using default summary statistics for continuous variables.
- Any post-baseline PCI result for each variable.
- If participants have PCI assessments, both below and above PCI criteria (as indicated in Table 10), participants are counted in both categories for summary tables.

A listing of all vital signs data including derived absolute change from baseline will be provided for the Safety Analysis Set.

